4.1.8.2 Presentation

Treatment compliance will be summarized separately for the OLP and the RTP, overall and by treatment group.

4.1.9 COVID-19 Impact

4.1.9.1 **Definitions and Derivations**

See section 3.3.9 for the definition.

4.1.9.2 Presentation

Depending on the extent of any impact, summaries of data relating to subjects diagnosed with COVID-19, and the impact of COVID-19 on study conduct may be generated including

- Disposition (discontinued IP due to COVID-19 and withdrew study due to COVID-19)
- Deviations (overall deviations plus if due to COVID-19 and not due to COVID-19)
- Summary of COVID-19 disruptions (visit impact, drug impacted)

Listing for subjects affected by the COVID-19 pandemic will also be produced.

4.2 Endpoint/Variable Analyses

This section covers details related to the endpoint analyses such as primary, secondary, other endpoints including sensitivity and supportive analyses.

Efficacy analyses will be undertaken for the open-label initial phase and the 28-day randomized treatment study phase on the respective full analysis sets unless otherwise stated.

STATISTICAL ANALYSIS PLAN

Statistical category	Endpoint	Analysis set	Intercurrent event strategy	Population level summary (analysis)	Details in section		
Primary objective: To even normokalemia (serum pota for hyperkalemic subjects of	Primary objective: To evaluate the efficacy of two different doses (5 and 10 g) of ZS orally administered once daily (qd) for 28 days in maintaining normokalemia (serum potassium [S-K] between 3.5-5.0 mmol/L, inclusive) in normokalemic subjects, following treatment in the open-label initial phase, for hyperkalemic subjects (two consecutive i-STAT potassium values \geq 5.1 mmol/L, taken 60 minutes apart) at baseline.						
Primary	Mean S-K level between placebo and each ZS treatment group (high to low) during the 28-day randomized treatment study phase Days 8-29.	FAS-RTP	Treatment policy: intercurrent events ignored	Difference in mean S-K values between each of the active treatment groups (ZS 10g and ZS 5g) and placebo, during RTP Days 8-29, estimated using a longitudinal mixed model.	4.2.1.4		
Sensitivity	Mean i-STAT level between placebo and each ZS treatment group (high to low) during the 28-day randomized treatment study phase Days 8-29.	FAS-RTP	Treatment policy: intercurrent events ignored	Difference in mean i-STAT values between each of the active treatment groups (ZS 10g and ZS 5g) and placebo, during RTP Days 8-29, estimated using a longitudinal mixed model.	4.2.1.5		
Supplementary	Mean S-K level between placebo and each ZS treatment group (high to low) during the 28-day randomized treatment study phase Days 8-29.	FAS-RTP	Hypothetical strategy for disallowed medications: measurements obtained while a subject was using disallowed medication are excluded from the analysis.	Difference in mean S-K values between each of the active treatment groups (ZS 10g and ZS 5g) and placebo, during RTP Days 8-29, estimated using a longitudinal mixed model.	4.2.1.6		
Secondary objective 1 (OLP): To evaluate the proportion of subjects who achieve normokalemia after the completion of open-label initial phase treatment							
Secondary	1- Proportion of subjects who achieve normokalemia (3.5 – 5.0 mmol/L) during and at the end of OLP (classification of each screened subject as	FAS-OLP	Treatment policy: intercurrent events ignored. This policy will be used for all four of the endpoints in this section.	 1- Probability of subjects achieving normokalemia, at 24 h and at the end of OLP, estimated as proportion of responders, with 95% two-sided Clopper-Pearson exact CIs. 2- The time effect derived from 	4.2.2.4		

STATISTICAL ANALYSIS PLAN D9480C00001 – ed. 3.0

Statistical category	Endpoint	Analysis set	Intercurrent event strategy	Population level summary (analysis)	Details in section
	 either a "responder" or a "non-responder") 2- Exponential rate of change in S-K levels during OLP 24 hours post-dose 3- Mean change (absolute and percent change) in S-K level at all post-dose time intervals during OLP 4- Time to normalization in S-K levels during OLP 			a longitudinal mixed model including all SK measurements up to 24 hours post-dose 3- Mean change (absolute and percent change) in S-K level from baseline to each of the planned measurement occasions during OLP, as well as end of OLP, analyzed using one sample, two-sided t-tests 4- The CDF of time to S-K normalization estimated using Kaplan-Meier life table curves	
Supplementary	Proportion of subjects who achieve normokalemia without use of disallowed medications during and at the end of OLP	FAS-OLP	Composite strategy: Intercurrent event (use of disallowed medication) is included as part of a composite endpoint, where subjects can only be counted as a "success" (responder) if they did not receive any disallowed medication before the measurement occasion and if they are normokalemic (S-K between 3.5-5.0 mmol/L).	Probability of subjects achieving normokalemia without usage of disallowed medications, estimated as proportion of responders, with 95% two-sided Clopper- Pearson exact CIs.	4.2.2.5
Supplementary	Mean change in S-K level from baseline to 24h and end of OLP	FAS-OLP	Hypothetical strategy: measurements obtained post usage of disallowed medications are removed from the analysis	Mean change in S-K level from baseline to 24h and end of OLP, analyzed using one sample, two-sided t-tests	4.2.2.5
Supplementary	Exponential rate of change in S-K levels during OLP 48 hours	FAS-OLP	Treatment policy: intercurrent events ignored.	The time effect derived from a longitudinal mixed model including all SK measurements	4.2.2.5

STATISTICAL ANALYSIS PLAN

Statistical category	Endpoint	Analysis set	Intercurrent event strategy	Population level summary (analysis)	Details in section				
	post-dose			up to 48 hours post-dose					
Secondary objective 2 (R	TP): To evaluate the effication	cy of ZS in subje	cts with hyperkalemia for the following	ng subgroups as applicable:					
- chronic kidney disease	e (CKD)								
- diabetes mellitus (DM	diabetes mellitus (DM)								
- heart failure (HF)									
- those on renin-angiote	ensin-aldosterone system (RA	AAS) inhibitors.							
Secondary	 Proportion of subjects who remain normokalemic during and at the end of RTP The number of days subjects remain normokalemic during RTP Time to hyperkalemia Mean change (absolute and percent change) in S-K level at all post-dose time intervals during RTP 	FAS-RTP	Treatment policy: intercurrent events ignored. This policy will be used for all four of the endpoints in this section.	 1- Odds ratio of being normokalemic on Day 29, and between Day 8 and 29, compared between each of the active treatment groups (ZS 10g and ZS 5g) and placebo using a logistic regression model (generalized random effect model) 2- The least square mean of number of the days will be compared between each of the active treatment groups (ZS 10g and ZS 5g) and placebo using a linear regression model 3- Hazard ratio for median time (days) to hyperkalemia between each of the active treatment groups (ZS 10g and ZS 5g) and placebo obtained from Cox proportional hazards model 4- Mean change (absolute and percent change) in S-K level 	4.2.3.3				
				trom baseline to each of the planned measurement occasions					

STATISTICAL ANALYSIS PLAN D9480C00001 – ed. 3.0

Statistical category	Endpoint	Analysis set	Intercurrent event strategy	Population level summary (analysis)	Details in section
				during RTP, analyzed using one sample, two-sided t-tests	
Supplementary	Proportion of subjects who remain normokalemic at the end of RTP	FAS-RTP	Composite strategy: Intercurrent event (use of disallowed medication) is included as part of a composite endpoint, where subjects can only be counted as a "success" (responder) if they did not receive any disallowed medication before the measurement occasion and if they are normokalemic (S-K between 3.5-5.0 mmol/L).	Odds ratio of being normokalemic on Day 29 compared between each of the active treatment groups (ZS 10g and ZS 5g) and placebo using a logistic regression model	4.2.3.4
Secondary objective 3 (R	TP): To evaluate the effect	of ZS on serum-A	Aldosterone (S-Aldo) and Plasma-Ren	nin (P-Renin) levels.	
Secondary	The mean changes in S- Aldo and P-Renin levels during RTP	FAS-RTP	Treatment policy: intercurrent events ignored.	Mean difference in values between each of the active treatment groups (ZS 10g and ZS 5g) and placebo estimated using a longitudinal mixed model.	4.2.3.3

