8.4.2 Secondary efficacy variables

For the open-label initial phase, the secondary efficacy endpoints will include the following parameters:

- Exponential rate of change in S-K levels (blood)
- Mean change (absolute and percent (%) change) from baseline in S-K levels at all measured time intervals post dose (See Table 1)
- Proportion of patients who achieve normokalemia during the open-label initial phase at 24 hours and at the end of the open-label phase
- Time to normalization in S-K levels (normalization defined as S-K levels between 3.5-5.0 mmol/L, inclusive)

For the subsequent 28-day randomized treatment study phase, the secondary efficacy endpoints will include the following parameters:

- The proportion of patients who remain normokalemic (as defined by S-K levels between 3.5-5.0 mmol/L, inclusive) at the end of the 28-day randomized treatment study phase and during the 28-day randomized treatment study phase
- The number of days patients remain normokalemic during the 28-day randomized treatment study phase
- The mean change and mean percent change in S-K levels evaluated relative to both the open-label initial phase and the 28-day randomized treatment study phase baselines, respectively
- The time to hyperkalemia (defined as $S-K \ge 5.1 \text{ mmol/L}$)
- The mean changes in S-Aldo and P-Renin levels

In this study, the following safety data will be collected: adverse events (AEs), vital signs, physical examinations, ECGs, clinical laboratory evaluations, and other electrolytes (specifically, serum calcium [S-Ca], serum magnesium [S-Mg], serum sodium [S-Na], serum phosphate [S-PO4], serum bicarbonate [S-HCO3], and blood urea nitrogen [BUN]).

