8.5.2 Analysis of the secondary and additional variables

For the open-label initial phase, the mean and relative reduction in the secondary efficacy endpoints will be evaluated for all enrolled patients. The change from baseline will be assessed using a paired t-test, and a two-sided p-value ≤ 0.05 will be considered statistically significant.

The methods used to evaluate the secondary efficacy endpoints, for the 28-day randomized treatment study phase; to compare each active dose (high to low) vs. placebo control will be describe in the SAP.

Secondary efficacy endpoints will include:

- The proportion of patients who remain normokalemic (as defined by S-K between 3.5-5.0 mmol/L, inclusive) at the end of the 28-day randomized treatment study phase and during the 28-day randomized treatment study phase
- The number of days patients remain normokalemic during the 28-day randomized treatment study phase
- The mean change and mean percent change in S-K levels evaluated relative to both baselines
- The time to hyperkalemia (defined as $S-K \ge 5.1 \text{ mmol/L}$)
- The mean change in S-Aldo and P-Renin levels

In addition, the secondary efficacy endpoint at the end of the 28-day randomized treatment study phase will be evaluated in patients with hyperkalemia (defined as S-K \geq 5.1 mmol/L) for the subgroups defined in Section 8.5.4. More details will be specified in the SAP.

Sensitivity analysis

Sensitivity analyses of the primary efficacy analysis and secondary efficacy analysis of the proportion of normokalemic patients at the end of and during the 28-day randomized treatment study phase will be performed to assess the robustness of the primary and these key secondary results. Details will be provided in the SAP.

Separate safety analyses will be performed for the open-label initial phase and the 28-day randomized treatment study phase. Safety endpoints will include adverse events (AEs), serious AEs (SAEs), vital signs (VS), physical examinations, ECGs, clinical laboratory evaluations, and other electrolytes (specifically, serum calcium [S-Ca], serum magnesium [S-Mg], serum sodium [S-Na], serum phosphate [S-PO4], serum bicarbonate [S-HCO3], and blood urea nitrogen [BUN]).

Hypokalemia will be analyzed based on laboratory values and not by specific MedDRA terms.

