2 CHANGES TO PROTOCOL PLANNED ANALYSES

The text referring to a 2-sample t-test in section 8.5 of the CSP, ("Where applicable, comparisons between each active dose treatment group vs. placebo control group will be performed using a 2-sample t-test.") has been removed as needed in the SAP, as this referred to the descriptive tabulations of data, and this is no longer part of the planned descriptive tabulation of the study.

The structure of the model used for the main analysis of the primary endpoint has been amended to include visit, treatment, as well as visit-by-treatment interaction as fixed effects, to reflect the corresponding analysis done in the Harmonize Global study. In addition, rather than incorporating a random intercept within subject explicitly in the model, an unstructured marginal covariance matrix will be used. This is to provide better potential for achieving good model fit (note that a model with a random intercept within subject and an e.g. scaled identity as conditional covariance matrix is a special case of this approach).

The subgroup analysis of the primary endpoint has been amended to assess all subjects, rather than those with hyperkalemia (S-K \geq 5.1mmol/L). This reflects the corresponding analysis in the Harmonize Global study and aligns with the primary analysis of the primary outcome.

Change from baseline in the OLP has been amended to use a one-sample, two-sided, t-test instead of a paired, two-sided, t-test. This allows a comparison of the mean change from baseline to the null hypothesis of zero (i.e. no change from baseline) rather than assessing the difference between the paired observations. This also aligns with the approach taken in the Global Harmonize study.

To better reflect the Intent-to-Treat (ITT) approach defined to the efficacy analyses the secondary endpoint reading:

D9480C00001 - ed. 3.0

 "Proportion of subjects who remain normokalemic (as defined by S-K between 3.5-5.0 mmol/L, inclusive) during the 28-day randomized treatment study phase at Study Days 29/Exit"

has been changed to:

"Proportion of subjects who remain normokalemic (as defined by S-K between 3.5-5.0 mmol/L, inclusive) during the 28-day randomized treatment study phase at Study Days 29".

To reflect the flexibility of the duration of the open label phase introduced in the later versions of the CSP the endpoint reading:

- "Open-label phase mean change from baseline of S-K 48 hours after first dose of ZS 10g"

has been clarified to state:

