3.3.1 General Study Level Definitions

3.3.1.1 Definition of Baseline Efficacy Baseline

For the OLP: The baseline Serum Potassium (S-K) will be established on the OLP Study Visit 3 (pre-dose) by taking the mean of 2 different S-K values.

For the RTP: The baseline S-K, S-Aldo and P-Renin will be established based on the last prerandomization measurement for S-K, S-Aldo and P-Renin, respectively, obtained during the OLP.

If baseline S-K C-lab values are missing, the i-STAT data will be used to replace them as described in Section 4.2.1.3. Subjects with missing values at baseline will be excluded from the relevant efficacy analysis.

Safety Baseline

Safety analyses will be performed separately for OLP and RTP. For change from baseline tabulations (laboratory measurements, vital signs, ECG and weight) the baseline will be defined as follows:

For OLP: Baseline will be the last non-missing measurement taken prior to first IP administration during OLP. If a measurement was taken on the date of first IP administration and no time is recorded, it is assumed that the measurement was taken pre-dose and will be considered a candidate for baseline.

For RTP: Same as OLP baseline, i.e. the last non-missing measurement taken prior to first IP administration during OLP.

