3.3.2.2 Secondary hypotheses

For the OLP, the following hypotheses will be tested versus two-sided alternatives:

Endpoint: Exponential rate of change in S-K levels (blood) at 24 hours and 48 hours during OLP.

The null hypothesis:

$$H_0$$
: Exponential rate A_{S-K} (24 hours) = 0 vs. H_A : Exponential rate A_{S-K} (24 hours) $\neq 0$

 H_0 : Exponential rate $\Delta S-K$ (48 hours) = 0 vs. H_A : Exponential rate $\Delta S-K$ (48 hours) $\neq 0$

This is evaluated by the parameter estimate of time (in hours) from a mixed effects model as described in Section 4.2.2.4. Note that the exponential rate of change refers to the degree of decline in SK values over time, which is assumed to follow an exponential trend.

Endpoint: Mean change (absolute and percent (%) change) from baseline in S-K levels

The null hypotheses:

$$H_0: \mu_{\Delta S-K} (24 \text{ hours}) = 0 \text{ vs. } H_A: \mu_{\Delta S-K} (24 \text{ hours}) \neq 0$$
$$H_0: \mu_{\Delta S-K} (End \text{ of } OLP) = 0 \text{ vs. } H_A: \mu_{\Delta S-K} (End \text{ of } OLP) \neq 0$$

The end of OLP can be 24 or 48 hours depending on the duration of OLP, as subjects who did not achieve normokalemia at 24 hours are evaluated again at 48 hours.

There will be a similar hypothesis for the mean percent change of S-K at 24 and 48 hours.

For the RTP, the following hypotheses will be tested:

Endpoint: Proportion of subjects who remain normokalemic at the end of the RTP and during the RTP.

The null hypotheses:

$$H_0: OR \left(ZS_{10g} vs Placebo \right) = 1. vs. H_A: OR \left(ZS_{10g} vs Placebo \right) \neq 1$$
$$H_0: OR \left(ZS_{5g} vs Placebo \right) = 1. vs. H_A: OR \left(ZS_{5g} vs Placebo \right) \neq 1$$

For each of the treatment arm comparisons, two tests will be done: one aiming at evaluating the odds of being normokalemic Day 8-29, performed by means of a generalized random effects model as described in Section 4.2.3, and another aiming at evaluating the probability of being normokalemic at Day 29 in particular, performed by means of a logistic regression model.

Endpoint: Number of days subjects remain normokalemic during the RTP.

The null hypotheses:

 $H_0: \mu_{\text{days of normokalemic}}(ZS_{10g}) = \mu_{\text{days of normokalemic}}(Placebo) \text{ vs.}$ $H_A: \mu_{\text{days of normokalemic}}(ZS_{10g}) \neq \mu_{\text{days of normokalemic}}(Placebo)$

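### The SAP table assigns one-sample t-tests to change in serum potassium during the randomized phase, a secondary endpoint that the protocol says is to be compared with placebo

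*SAP*

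**What the plan says.** **Protocol.** Section 8.5.2 lists among the randomized-phase secondary endpoints "The mean change and mean percent change in S-K levels evaluated relative to both baselines". Section 8.4.2 names the baselines: "evaluated relative to both the open-label initial phase and the 28-day randomized treatment study phase baselines, respectively". On method, 8.5.2 says that the approach "to compare each active dose (high to low) vs. placebo control will be describe in the SAP".

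**SAP 4.2, summary table.** Under secondary objective 2, four randomized-phase endpoints share one row. The first three (normokalemia, normokalemic days, time to hyperkalemia) each carry an explicit ZS-versus-placebo contrast. The fourth, change in S-K, is "during RTP, analyzed using one sample, two-sided t-tests". The entry for the single-arm open-label phase has almost the same wording: "during OLP, as well as end of OLP, analyzed using one sample, two-sided t-tests".

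**Elsewhere in the SAP.**
- Section 4.2.3.3, to which the table refers, mentions S-K change only among descriptive statistics. Section 4.2.1.4 likewise only summarizes it by group.
- The list of randomized-phase secondary endpoints in 4.2.3.1 does not include it.
- Section 3.3.2.2 opens its list with "For the RTP, the following hypotheses will be tested", and no hypothesis for S-K change follows.
- Section 2 declares: "Change from baseline in the OLP has been amended to use a one-sample, two-sided, t-test". It says nothing equivalent for the randomized phase. It also removes the protocol's general 2-sample t-test, on the ground that this concerned descriptive tabulations.
- Section 3.3.1.1 defines an open-label efficacy baseline, and for the randomized phase says: "The baseline S-K, S-Aldo and P-Renin will be established based on the last prerandomization measurement". The text on randomized-phase change does not say that both are used.

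**The concern.** A one-sample test asks whether mean change within one arm differs from zero. In the open-label phase, where everyone receives the same treatment, that is the only question available. In the randomized phase the protocol's question is whether ZS differs from placebo, and a test within each arm does not answer it. A drift shared by all arms can give small p-values everywhere with no treatment effect. A ZS arm that holds potassium flat gives a large p-value even if placebo rises.

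The problem is plainest for change from the open-label baseline. The fall produced by open-label ZS occurs before randomization in every arm, so a within-arm test from that baseline largely reflects treatment that all arms received.

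At stake is the reporting of one secondary endpoint. The only inferential method named for it cannot show a treatment effect, and the change from the protocol's intention is not declared.

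**Working it through.** **Side by side**

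| Place | Treatment of randomized-phase S-K change |
|---|---|
| Protocol 8.4.2, 8.5.2 | Secondary endpoint, both baselines, each dose vs placebo |
| SAP 4.2 table | One-sample two-sided t-tests |
| SAP 4.2.3.3, 4.2.1.4 | Descriptive |
| SAP 4.2.3.1, 3.3.2.2 | Not listed |
| SAP 2 | One-sample test declared for the open-label phase only |

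Read literally, the table covers nine post-baseline visits (Days 2, 5, 8, 12, 15, 19, 22, 26, 29). That gives 9 × 3 arms × 2 scales = 54 tests per baseline, or 108 with both baselines. None compares ZS with placebo.

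**Inputs.** Protocol 8.2: 100 patients per ZS arm, 50 on placebo, SD 0.50 for mean S-K, planning difference 0.30, planned open-label fall 1.05, two-sided 5%. The documents give no SD for change. I assume 0.40 to 0.60 and show 0.70 as a check. The common shift of 0.20 is also an assumption.

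**The plan's own figure.** For a between-arm t-test, the noncentrality is δ / (σ√(1/100 + 1/50)) = 0.30 / (0.50 × 0.1732) = 3.46 on 148 df. Power is 93.1%, which agrees with the stated figure of more than 90%.

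**Formula for the one-sample test.** The noncentrality is δ√n / σ on n − 1 df. At δ = 0.20 and σ = 0.50 it is 0.20 × 10 / 0.50 = 4.00 for n = 100, and 0.20 × 7.07 / 0.50 = 2.83 for n = 50.

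**Scenario 1: every arm shifts by 0.20, no treatment effect**

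| SD of change | ZS arm rejects (n=100) | Placebo rejects (n=50) | Between-arm test rejects |
|---|---|---|---|
| 0.40 | 99.9% | 93.4% | 5% |
| 0.50 | 97.7% | 79.2% | 5% |
| 0.60 | 91.0% | 63.7% | 5% |

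**Scenario 2: ZS flat, placebo rises by 0.30**

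| SD of change | ZS one-sample rejects | Between-arm test rejects |
|---|---|---|
| 0.40 | 5% | 99.0% |
| 0.50 | 5% | 93.1% |
| 0.60 | 5% | 81.8% |

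Per-visit change may vary more than a mean over several visits. At SD 0.70 the ZS one-sample test in scenario 1 rejects in 81%, and the between-arm test in scenario 2 in 69%. The pattern stays.

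**Scenario 3: change from the open-label baseline, placebo arm (n=50).** Solving for the residual fall that gives 80% rejection yields 0.162, 0.202 and 0.243 at SD 0.40, 0.50 and 0.60. The share of the planned fall already lost is 1 − 0.162/1.05 = 84.6%, 1 − 0.202/1.05 = 80.8% and 1 − 0.243/1.05 = 76.9%. A placebo arm that has lost about four fifths of the open-label effect would still usually show a small p-value for change from baseline.

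**Check of the remedy.** If both baseline S-K values are covariates, subtracting either one from the response alters only that baseline's own coefficient. On one simulated data set the arm coefficient was −0.3548 (SE 0.0708) for S-K level, for change from the open-label baseline and for change from the randomized-phase baseline. For percent change the two baselines gave −6.40% and −7.70%, so percent change needs its own fits.

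**The case against.** The strongest reply is that little depends on this. The endpoint is outside the hierarchy, and SAP 3.3.7 makes such p-values exploratory and says that they will not be called significant. The primary model (3.3.6, 4.2.1.4) compares each dose with placebo on log S-K over Days 8-29, adjusted for both baselines, and reports the back-transformed relative difference. The covariate identity above means that a model of absolute change is close to that contrast refitted in mmol/L. All of this stands and limits the weight of the point. What the primary model does not supply is the difference in mmol/L, the percent change from each baseline, or anything before Day 8.

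Second, the phrase looks like a carry-over from the open-label row, since the section that it cites contains no such test. That is plausible, and it is a reason to correct the table. The table nevertheless classes the endpoint as secondary and names a test.

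Third, Section 2 does remove the protocol's 2-sample t-test. A reader might therefore say that the loss of the placebo comparison was declared. It is the nearest thing to a declaration, but it is confined to descriptive tabulations and does not name this endpoint. Nor is there a general policy against contrasts for change endpoints: aldosterone and renin keep theirs in 4.2.3.3.

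Fourth, the protocol chose the log scale because it expects log-normal potassium and wants a stable variance. That is fair for the primary analysis. This endpoint, however, is defined as absolute and percent change, and the added model would only be supportive.

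**Conclusion.** The point holds as a defect in the specification of one exploratory secondary endpoint. The protocol calls for a placebo comparison from both baselines. The SAP table names a test that cannot provide one, the rest of the SAP is descriptive or silent, and the departure is not declared.

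A reader might go further and infer that the SAP has no placebo comparison of potassium in the randomized phase, or that error control or the primary conclusion is at risk. The documents do not support that. The primary model makes the comparison, and these tests have no place in the hierarchy.

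The rejection rates are illustrations, not predictions. They rest on an assumed SD of change (0.40 to 0.60, or 0.70 as a check) and, in scenario 1, an assumed shift of 0.20. The conclusion that a within-arm test does not estimate a treatment effect needs neither assumption. The plan should be corrected, but nothing confirmatory depends on it.

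**What to change.** In the SAP 4.2 table and in 4.2.3.3:
- Delete the randomized-phase one-sample t-tests.
- Give ZS 10 g minus placebo and ZS 5 g minus placebo, with 95% confidence intervals, at each planned visit from Day 2 to Day 29 and overall for Days 8-29. Days 2 and 5 are needed because the table defines the endpoint at every planned occasion.
- Use a supportive mixed model in mmol/L with treatment, visit, treatment-by-visit and the primary model's covariates, including both baseline S-K values. One set of contrasts then serves absolute change from either baseline.
- Fit percent change from each baseline separately.
- Report within-arm change from each named baseline descriptively, without p-values.

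Add the endpoint to 4.2.3.1 and label it exploratory.

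If the sponsor prefers description only, the minimum is to delete the one-sample tests and declare in Section 2 the departure from protocol 8.5.2.

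The cost is a few lines of SAP text and, under the fuller option, one supportive model for absolute change and one for percent change from each baseline. No new data are needed.
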